8. STATISTICAL CONSIDERATIONS

8.1. General Considerations

This section outlines the data summaries and analyses that will be specified in the applicable analysis plan and included in a CSR. A CSR statistical analysis plan (SAP) and separate PK SAP will be prepared and finalized by the Sponsor prior to each database lock. In addition, Biomarker SAPs will be prepared as required. Also, specifications will be prepared by the Independent Reporting Statistical Group and independent exposure-response analyst for the dose selection analyses and data reviews described in Section 8.10, Independent Data Monitoring Committee.

The following formal analyses are planned:

- Analyses of Phase 2b Induction data after all subjects have either completed the Week 8 assessments or prematurely withdrawn from the study
- Analyses of Phase 3 Induction data
- Analyses of Phase 3 Maintenance data, with primary efficacy summaries restricted to placebo and the maintenance doses selected for continued evaluation based on the Induction Phase 2b dose selection analyses

Prior to each analysis, the database for the relevant study will be cleaned and locked.

Study Day 1 is defined as the day of the first study drug dose. The preceding day is Study Day -1. For the Phase 3 Maintenance Study, Study Day 1 is defined as the day of the first Maintenance study drug dose.

All data for each subject will be listed as collected. All statistical summaries and analyses will be performed using [REDACTED].

Quantitative data and scores (e.g., adapted Mayo score) will be summarized using an 8-point summary (n, mean, standard deviation [SD], median, interquartile range [25th percentile Q1, 75th percentile Q3], minimum, and maximum) unless otherwise specified in the SAP or table shell. Categorical data will be summarized using counts and percentages.

In general, baseline is the last value (scheduled or unscheduled) obtained before the start of study drug dosing. For efficacy endpoints, baseline for those having more than one component (e.g., adapted Mayo score) is calculated from the individual component baselines, whether or not they were assessed during the same visit, and baseline at Maintenance study entry is the value at the last Induction study visit (Week 8 or Week 16).

Values that are derived from symptom diary data will be derived from the last 3 consecutive days for which evaluable data are available during the 7 days preceding the visit; this applies to both baseline and postbaseline values. If not found, values will be derived from the 3 most recent days for which evaluable data are available.

Any changes to the data summaries and analyses outlined in this section will be described in the applicable SAP. Any major changes to primary and key secondary endpoints will be described in a protocol amendment.

8.2. Sample Size and Power

It is currently estimated that approximately 880 subjects (240 for Phase 2b Induction and 640 for Phase 3 Induction) will be enrolled.

The number of enrolled subjects is expected to provide at least 90% power for the primary endpoints of the Induction Studies and also allow a sufficient number of subjects eligible for re-randomization into the Phase 3 Maintenance Study because:

1. A subset of subjects from the initial Phase 3 Maintenance study before final dose selection is determined will be excluded from the analysis of primary and secondary efficacy endpoints: i.e., the subjects assigned to doses that were not selected.
2. Only subjects who received TD-1473 and are considered responders after 8 weeks of Induction therapy, including subjects who are randomized to placebo during the first 8 weeks of Induction Therapy who demonstrate clinical response at Week 16 after receiving TD-1473 80 mg from Weeks 9 to 16, are eligible to be re-randomized in the Phase 3 Maintenance study.
3. The average responder rate for the active treatment groups is estimated to be 60%.
4. It is also estimated that approximately 10% of subjects who are eligible to be re-randomized into the Phase 3 Maintenance study will elect not to participate.

8.2.1. Induction Phase 2b Sample Size Considerations

A sample size of 60 subjects per group was estimated to give approximately 90% (89%) power to detect a 2-point active dose group vs. placebo improvement in total Mayo score at all three doses, given the following:

- Hochberg step-up procedure adjustment for multiple comparisons, with family-wise type 1 error rate to be controlled at 5% (2-sided tests)
- Residual change SD of 3 points

The estimated power to detect a 2-point improvement relative to placebo for at least one of the three doses was greater than 98%.

Assuming a slightly higher residual change SD of 3.5 points, the estimated power to detect a 2-point active dose group vs. placebo improvement in total Mayo score at all three doses was approximately 73% and the estimated power to detect a 2-point improvement at one or more of the doses was approximately 94%. Estimates were obtained using East software, with 10,000 simulations per case.

Subjects will be stratified by prior biologics failure and baseline corticosteroids use at randomization. In addition, randomization caps will be placed on both prior biologics failure subgroups [no to biologics failure (60%) and yes to biologics failure (60%)] to ensure that neither subgroup is overrepresented.

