6.6.2. Subject Replacement

At the Sponsor's discretion, subjects who withdraw or are withdrawn before taking study drug may be replaced. Should greater than 10% of treated patients withdraw before the primary endpoint visit or miss the primary endpoint visit due to events that could not be foreseen during study design planning (e.g., COVID-19 pandemic) then treated subjects may be replaced. Safety data will be presented for all subjects in the Clinical Study Report (CSR) regardless of whether the subject was a replacement.

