8.9. Data Handling Rules

For primary analyses of all applicable efficacy endpoints, including secondary and additional endpoints, the following rules will be applied. For sensitivity analyses of primary and key secondary endpoints, different rules may be specified in the applicable SAP.

- Binary endpoints: Subjects who had non-missing data for a binary efficacy endpoint meeting the criterion for success but met definition of treatment failure prior to visit will be considered as not meeting endpoint. Full rules for the derivation of treatment failure will be outlined in the SAP.
- Missing = endpoint not met

Quantitative or score endpoints:

- The treatment failure criteria above are applied to exclude any assessments obtained following treatment failure
- MMRM analysis with data assumed to be “Missing at Random” for quantitative or score endpoints assessed more than once postbaseline
- The analysis of the Phase 2b primary endpoint will be a completers analysis. For other quantitative or score endpoints assessed only once post-baseline, imputation for missing data will be described in the SAP.

[REDACTED]

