1.5. Sample Size Determination

A sample size of 60 subjects per group is estimated to give approximately 90% power to detect a 2 point improvement relative to placebo in total Mayo score at all three doses, under the following assumptions:

- Hochberg step-up procedure adjustment for multiple comparisons (2-sided tests)
- Family-wise type 1 error rate to be controlled at 5%
- Residual change standard deviation (SD) of 3 points

The estimated power to detect a 2-point improvement relative to placebo for at least one of the three doses is greater than 98%.

Assuming a slightly larger residual change SD of 3.5 points, the estimated power to detect a 2 point active dose group vs. placebo improvement in total Mayo score at all three doses was approximately 73% and the estimated power to detect a 2 point improvement at one or more of the doses was approximately 94%.

Estimates were obtained using East software, with 10,000 simulations per case.

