2. ANALYSIS SETS

Table 3: Analysis Sets

Analysis Set	Definition	Treatment Assignment
Screen Failures	Subjects who give informed written consent but are not randomized are considered screen failures. Screen failure subjects and the main reason for screen fail will be captured in the EDC.	N/A
Safety*	The Safety analysis set will include all subjects who received at least one dose of study drug (TD-1473 or placebo). The Safety analysis set is the primary analysis set for safety analyses.	Actual Treatment received (see Section 3.1.6)
ITT*	The Intent-to-Treat (ITT) analysis set comprises all randomized into the Phase 2b study.	Randomized treatment
Modified ITT*	The modified Intent-to-Treat (mITT) analysis set comprises all randomized subjects who receive at least one dose of study drug. The mITT set is the primary analysis set for efficacy summaries and analyses.	Randomized treatment
Modified ITT-16w*	The modified Intent-to-Treat for extended induction (mITT-16w) analysis set comprises all randomized into the Phase 2b study, who did not meet the criteria for clinical response by adapted Mayo score at Week 8, and, continued dosing during extended induction.	Randomized treatment
PP*	The Per-Protocol (PP) analysis set comprises all subjects in the mITT analysis set who complete their Week 8 visit and have no major analysis protocol deviations	Randomized treatment

- Due to confirmed data integrity violations the data for site 36044 (deviation report GCP-23) and site 38915 (deviation report GCP-11) will be excluded from all analysis sets.

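### The stated Phase 2b power assumes that all 60 randomised subjects per arm are analysed; no loss is allowed for, and 10% loss would cut the all-three-dose power from 89% to about 84%

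*Protocol*

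**What the plan says.** Protocol 8.2.1 states: "A sample size of 60 subjects per group was estimated to give approximately 90% (89%) power". The power in question is "power to detect a 2-point active dose group vs. placebo improvement in total Mayo score at all three doses", with Hochberg's procedure holding the family-wise error at 5% two-sided and "Residual change SD of 3 points". The same section gives more than 98% for at least one dose and, at SD 3.5, about 73% and 94%. The synopsis and Phase 2b SAP 1.5 repeat this; the SAP wording is "A sample size of 60 subjects per group is estimated to give approximately 90% power".

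The 60 per group is the randomised number: Protocol 3.1 enrols approximately 240 subjects 1:1:1:1 to placebo and three doses. Protocol 8.2 goes further and attaches at least 90% power for the Induction Studies' primary endpoints to the number enrolled.

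On who is analysed, Protocol 8.9 says: "The analysis of the Phase 2b primary endpoint will be a completers analysis". Protocol 8.5.4 leaves missing Week 8 scores unimputed. SAP 3.3.2 modifies this: the Week 8 total Mayo score is calculated if at least one of its four components is present, with the others carried forward. SAP 3.3.4.3 leaves whatever is still missing unimputed. SAP section 2 adds that the data of two sites "will be excluded from all analysis sets" because of data-integrity violations.

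On replacement, Protocol 6.6.2 allows it for subjects who leave before taking study drug. For treated subjects the condition begins "Should greater than 10% of treated patients withdraw before the primary endpoint visit or miss the primary endpoint visit", and it is limited to losses from events that could not have been foreseen at planning. Replacement is then optional.

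**The concern.** A power calculation describes the subjects who enter the analysis. Here one number, 60, serves as both the randomised and the analysed count, although the plan foresees a gap between them. The primary analysis waits until every subject has completed Week 8 or left before it, and SAP 3.3.6.5 tabulates subjects with every Week 8 component missing, split into early discontinuation and missed visit. The Maintenance calculation does allow for loss (10% of eligible subjects declining entry in Protocol 8.2, about 30 on a de-selected dose in 8.2.3). The Phase 2b calculation has no counterpart.

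At stake is how the result is read. Phase 2b feeds dose selection (Protocol 8.11). Its outcome on all three doses would be judged against a stated 89% that applies only if nobody is lost.

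**Working it through.** **Inputs.** Difference δ = 2 points at each dose; σ = 3, or 3.5 in the alternative case; Hochberg at 5% two-sided over three comparisons with a shared placebo arm; n = 60 per arm (Protocol 8.2.1, SAP 1.5). The loss rate is not given in the documents. I assume 5%, 10% and 20%, equal across arms and unrelated to outcome.

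**Method.** For each dose k, t_k = (ȳ_k − ȳ_0) / (s·√(2/n)), with s pooled over four arms on 4(n − 1) degrees of freedom. The SD is described as residual, so the covariates are taken as already accounted for. Under Hochberg, all three doses are significant when the largest p-value is at most 0.05. At least one is significant when the largest is ≤ 0.05, or the middle one ≤ 0.025, or the smallest ≤ 0.05/3. Each case was simulated with 2,000,000 replicates.

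**Step 1: the plan's own figures, n = 60.** At σ = 3 the standard error of a difference is 3·√(2/60) = 0.548, so δ/SE = 3.65.

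| σ | Criterion | Stated | Simulated |
|---|---|---|---|
| 3 | all three | 89% | 88.9% |
| 3 | at least one | >98% | 98.4% |
| 3.5 | all three | about 73% | 73.9% |
| 3.5 | at least one | about 94% | 93.8% |

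All four reproduce with 60 analysed per arm, so no loss is built in.

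**Step 2: with loss.** Analysed number = 60 × (1 − loss): 57, 54 and 48. At σ = 3, δ/SE becomes 2/(3·√(2/57)) = 3.56, 2/(3·√(2/54)) = 3.46 and 2/(3·√(2/48)) = 3.27.

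| Loss | n per arm | σ = 3: all three / at least one | σ = 3.5: all three / at least one |
|---|---|---|---|
| 0% | 60 | 88.9% / 98.4% | 73.9% / 93.8% |
| 5% | 57 | 86.8% / 97.9% | 70.9% / 92.6% |
| 10% | 54 | 84.4% / 97.3% | 67.6% / 91.1% |
| 20% | 48 | 78.5% / 95.5% | 60.6% / 87.5% |

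The at-least-one figure is still 98.1% at 58 per arm and drops below the stated 98% at 57.

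**Step 3: power for one given dose after Hochberg, σ = 3.** About 94% at 60 per arm and 92% at 54.

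**Step 4: the statement in Protocol 8.2.** On the all-three criterion the enrolled number gives 88.9% even with no loss, so at least 90% is not met. On the at-least-one criterion at σ = 3 it is met throughout the range above. Section 8.2 does not say which criterion it means.

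**The case against.** Nothing is miscalculated: every stated figure reproduces. The sponsor also discloses a less favourable case, SD 3.5, whose 73% is lower than any σ = 3 entry in the table above. Both points stand. The issue is an unstated assumption.

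The SAP also keeps more subjects than the protocol's completers label suggests. One Week 8 component is enough to keep a subject, data after rescue or discontinuation are used as collected (SAP 3.3.4.1), and the Week 8 window runs from day 46 to as late as day 71 (SAP 3.1.3). Only subjects with no Week 8 component, plus the two sites, are lost. This limits the loss of numbers but does not fully protect power. Before Week 8 the only scheduled endoscopy is at screening, so a missing Week 8 endoscopy carries the baseline value forward and records no endoscopic change. As an illustration, assume that a quarter of the 2-point effect (0.5) is endoscopic and that 10% of subjects lack the Week 8 endoscopy. The mean difference is then 2 − 0.10 × 0.5 = 1.95. With all 60 kept and σ = 3, the all-three-dose power is about 87%.

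A reader might infer that the design delivers 84%, taking the 10% in Protocol 6.6.2 as an accepted dropout rate. The text does not support this. That 10% triggers optional replacement after unforeseeable events; it neither forecasts nor limits ordinary dropout. The 10% in Protocol 8.2 concerns entry to Maintenance. Nor can the two-site exclusion be turned into a loss, because the number of subjects at those sites is not given.

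**Conclusion.** The stated all-three-dose power of 89% is right for 60 analysed subjects per arm and too high for any smaller number. The plan randomises 60, leaves out subjects with no Week 8 component and two whole sites, does not replace ordinary dropout after dosing, and states no allowance. At SD 3 the overstatement is about 2 points at 5% loss, 4 to 5 points at 10% and 10 points at 20%. For at least one dose it is 0.5, 1 and 3 points. These sizes rest on assumed loss rates, on loss that is equal across arms and unrelated to outcome, and on the plan's own effect and SD.

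A reader might also conclude that a non-significant result on a single dose would be badly misjudged. That goes too far: at SD 3, per-dose power is still about 92% at 10% loss. The material shortfall is in the claim about all three doses together.

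**What to change.** In the synopsis, Protocol 8.2.1 and SAP 1.5, say that the power figures assume 60 analysed subjects per arm. State the expected number with a Week 8 score and the basis for it, and give the power at that number together with the 5%, 10% and 20% loss cases above, at SD 3 and SD 3.5. In Protocol 8.2, stop attaching at least 90% power to the enrolled number for Phase 2b, or name the criterion and the analysed number to which it applies. The Maintenance SAP records that the Phase 2b outcome is already known, so if the documents can no longer be amended, the same statement belongs in the clinical study report beside the number analysed per arm.

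The cost is a less favourable stated figure, with no added patients and no change to the analysis. Keeping 60 evaluable at 10% loss would have needed 60/0.9, rounded up to 67 per arm (268 in total). That is given for scale and is not proposed.

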8.2.2. Induction Phase 3 Sample Size Considerations

Upon completion of the analyses based on the Phase 2b Induction data, the sample size may be refined. Currently, it is estimated that 320 subjects per dose group (640 subjects total) will

provide at least 90% power to demonstrate TD-1473 is effective compared to placebo for the primary endpoint of clinical remission at Week 8 under the following assumptions:

- Type 1 error rate of 5% (2-sided)
- Clinical remission rate of 9.5% for placebo at Week 8
- Clinical remission rate of 23.5% for TD-1473 at Week 8:

It is also estimated that 320 subjects per group will provide at least 90% power to demonstrate TD-1473 is effective compared to placebo for the key secondary endpoints of symptomatic remission and endoscopic healing.

In the case where two TD-1473 doses are selected, then 320 subjects per group will have at least 90% disjunctive power to demonstrate at least one of the two TD-1473 doses is effective compared to placebo for clinical remission at Week 8 under the following assumptions:

- Hochberg step up procedure adjustment for multiple comparisons
- Family-wise type 1 error rate to be controlled at 5% (2-sided)
- Clinical remission rate of 9.5% for placebo at Week 8
- Clinical remission rate of 23.5% for more effective TD-1473 dose and 16.5% for the less effective TD-1473 dose

Subjects will be stratified by prior biologics failure and baseline corticosteroids use at randomization. In addition, randomization caps will be placed on both prior biologics failure subgroups (no to biologics failure (60%) and yes to biologics failure (60%)) to ensure that neither subgroup is overrepresented.

8.2.3. Phase 3 Maintenance Sample Size Considerations

Upon completion of the analyses based on the Phase 2b Induction data, the sample size may be refined. Currently, it is estimated that 120 subjects per dose group (360 subjects total) will provide at least 90% disjunctive power to demonstrate at least one of the two TD-1473 doses is effective compared to placebo for the primary endpoint of clinical remission at Maintenance Week 44 under the following assumptions:

- Hochberg step-up procedure adjustment for multiple comparisons
- Family-wise type 1 error rate to be controlled at 5% (2-sided)
- Clinical remission rate of 15% for placebo at Week 44
- Clinical remission rates of 30% and 40% for the two active TD-1473 doses at Maintenance Week 44

A total of 360 subjects total will provide 80% conjunctive power to demonstrate both doses of TD-1473 are effective compared to placebo for clinical remission at Maintenance. In addition, 360 subjects total will also provide adequate power (at least 80%) to demonstrate that at least one of the two TD-1473 doses is effective compared to placebo for the key secondary endpoints of symptomatic remission and endoscopic healing at Maintenance Week 44.

It is estimated that with 880 subjects enrolled in the Induction studies, approximately 400 subjects will be eligible for re-randomization into the Maintenance study. However, about 30 of these 400 subjects will be assigned to the dose that is de-selected based on the analyses of the Phase 2b Induction Study data and therefore not included in the primary efficacy analysis population of the Phase 3 Maintenance Study. In addition, approximately 170 subjects will also enter Maintenance and continue to receive the same treatment as assigned in the Induction study in order to maintain blind. These subjects will also not be included in the primary efficacy analysis population of the Phase 3 Maintenance Study.

8.3. Analysis Sets

8.3.1. Analysis Sets

For the Phase 2b Induction study and Phase 3 Induction study, the modified Intent-to-Treat (mITT) analysis set will include all randomized subjects who receive at least one dose of study drug. For the Phase 3 Maintenance study, the mITT analysis set comprises all randomized subjects who receive at least one dose of study drug and are assigned to receive either placebo or a TD-1473 dose selected based on the Phase 2b dose selection analyses, and the Full Analysis Set (FAS) comprises all randomized subjects who receive at least one dose of study drug. For each study, the mITT set is considered the primary analysis set for efficacy analyses.

The Per-Protocol (PP) analysis set comprises all subjects in the mITT analysis set with no major analysis protocol deviations (Section 8.3.3). Both the mITT and the PP analysis set will be used for selected efficacy summaries and analyses to be specified in the applicable SAP. In addition, for selected Induction Phase 2b dose-response analyses, a PP completers analysis set will be used. The PP completers analysis set comprises all subjects enrolled in the Induction Phase 2b Study with no major analysis protocol deviations and non-missing total Mayo score at Week 8.

The Safety analysis set comprises all subjects who receive at least one dose of study drug. The Safety analysis set will be the analysis set for general (baseline, exposure, and compliance) and safety analyses.

The PK analysis set will include all subjects in the Safety analysis set with at least one evaluable postbaseline TD-1473 PK measurement who are adherent to the protocol. Subjects may be excluded from the PK analysis set if they deviate significantly from the protocol or if the data are unavailable or incomplete, which may influence the PK analysis. The PK analysis set will be further defined in the PK SAP.

Except for the PK analysis set, which is restricted to subjects who received TD-1473, membership in each analysis set will be determined prior to database lock. Analyses using the mITT analysis set will be by randomized treatment. Analyses using the PP analysis set or the safety analysis set will be by actual treatment.

8.3.2. Examination of Subgroups

Predefined subgroups for the Phase 2b and Phase 3 Induction studies will include those defined by the randomization stratification variables:

- History of biologics failure at screening for the Induction study (Yes, No)

- Steroid use status at enrollment into the Induction study (Yes, No)

Additional subgroups may be defined in the applicable SAP.

Predefined subgroups for the Phase 3 Maintenance study likewise will include those defined by the randomization stratification variables:

- Clinical remission status (using adapted Mayo score component definition) at enrollment into the Maintenance study (Yes, No)
- Steroid use status at enrollment into the Maintenance study (Yes, No)

Additional subgroups may be defined in the applicable SAP, e.g., history of biologics failure group, randomization stratum, placebo non-responder who responded after 8 weeks on TD-1473, responder after 8 weeks.

For analysis purposes, values of randomization stratification variables will be determined from the information collected in the clinical database, rather than the information in the RTSM database.

